## 6.7.4.2 Clinical chemistry

Serum chemistry panel will be performed at the scheduled visits as indicated in Table 6-1 and includes: urea, creatinine, total bilirubin, alanine transaminase (ALT)/serum glutamic pyruvate transaminase (SGPT), aspartate transaminase (AST)/serum glutamic oxaloacetic transaminase (SGOT), gamma glutamyl transpeptidatse (GGT), and alkaline phosphatase.

## 6.7.4.3 High-sensitivity C-reactive protein

High-sensitivity C-reactive protein (hs-CRP) will be measured by the central laboratory at the scheduled visits as indicated in Table 6-1.

## 6.7.4.4 Hemoglobin A1c

Hemoglobin A1c (HbA1c) will be measured by the central laboratory at the scheduled visits as indicated in Table 6-1.

## 6.7.4.5 Fasting laboratory evaluations and HOMA-IR

Fasting (minimum 8 hour duration with water *ad libitum*) laboratory tests will be performed at scheduled visits as indicated in Table 6-1 and will include:

- plasma glucose
- insulin
- lipids

Homeostatic model assessment of insulin resistance (HOMA-IR) values will be reported by the central laboratory at the scheduled visits as indicated in Table 6-1.

## 6.7.4.6 Viral serology

Viral serology will be performed at screening and will include:

- Hepatitis screening: Hepatitis B surface antigen (HBsAg); Hepatitis C virus antibody (HCVAb)
- HIV screening: HIV 1/2

## 6.7.5 **Pregnancy and assessments of fertility**

All pre-menopausal women who are not surgically sterile will have a serum  $\beta$ -hCG test performed at screening (Visit 1).

All women of childbearing potential will also have a urine pregnancy test performed locally at Visit 2/Baseline. Visit 8/Week 12, and Visit 15/Week 52.

Any woman with a confirmed positive pregnancy test during screening is not eligible for randomization.

A positive urine pregnancy test during the study requires immediate interruption of study treatment until serum  $\beta$ -hCG is performed and found to be negative. If the serum  $\beta$ -hCG test is positive, the patient must be discontinued from the study as described in Section 5.6.2.

## 6.7.6 Appropriateness of safety measurements

The safety assessments selected for this study are reliable and standard measures for a biologic immunomodulating agent in adult patients with psoriasis.

## 6.8 Other assessments

No additional tests will be performed on patients entered into this study.

# 7 Safety monitoring

## 7.1 Adverse events

An adverse event (AE) is any untoward medical occurrence (e.g., any unfavorable and unintended sign [including abnormal laboratory findings], symptom or disease) in a patient or clinical investigation patient *after providing written informed consent* for participation in the study until the end of study visit. Therefore, an AE may or may not be temporally or causally associated with the use of a medicinal (investigational) product.

In addition, all reports of intentional misuse and abuse of the product are also considered an adverse event irrespective if a clinical event has occurred.

The occurrence of adverse events must be sought by non-directive questioning of the patient at each visit during the study. Adverse events also may be detected when they are volunteered by the patient during or between visits or through physical examination findings, laboratory test findings, or other assessments.

Abnormal laboratory values or test results constitute adverse events only if they fulfill at least one of the following criteria:

- they induce clinical signs or symptoms,
- they are considered clinically significant,

• they require therapy.

Clinically significant abnormal laboratory values or test results must be identified through a review of values outside of normal ranges/clinically notable ranges, significant changes from baseline or the previous visit, or values which are considered to be non-typical in a patient with underlying disease. Investigators have the responsibility for managing the safety of individual patients and identifying adverse events. Alert ranges for laboratory and other test abnormalities are included in Section 13 Appendix 1.

Confidential

Adverse events must be recorded in the Adverse Events CRF under the signs, symptoms or diagnosis associated with them, accompanied by the following information:

- the severity grade
  - mild: usually transient in nature and generally not interfering with normal activities
  - moderate: sufficiently discomforting to interfere with normal activities
  - severe: prevents normal activities
- its relationship to the study treatment
  - Yes
  - No
- its duration (start and end dates) or if the event is ongoing, an outcome of not recovered/not resolved must be reported
- whether it constitutes a serious adverse event (SAE see Section 7.2 for definition of SAE) and which seriousness criteria have been met
- action taken regarding study treatment

All adverse events must be treated appropriately. Treatment may include one or more of the following:

- no action taken (e.g. further observation only)
- study treatment dosage increased/reduced
- study treatment interrupted/withdrawn
- concomitant medication
- non-drug therapy given
- patient hospitalized/patient's hospitalization prolonged (see Section 7.2 for definition of SAE)
- its outcome (not recovered/not resolved; recovered/resolved; recovering/resolving, recovered/resolved with sequelae; fatal; or unknown)

Once an adverse event is detected, it must be followed until its resolution or until it is judged to be permanent, and assessment must be made at each visit (or more frequently, if necessary) of any changes in severity, the suspected relationship to the study drug, the interventions required to treat it, and the outcome.

Worsening of psoriasis in this study is evaluated via the use of the PASI and the evaluated with the evaluated via the use of the PASI and is not expected to be captured as an AE in the eCRF. Exceptions include cases where: a) a new type of psoriasis is diagnosed, e.g. guttate psoriasis, or b) the worsening of psoriasis is so severe that a qualitatively different status is reached.

Information about common side effects already known about the investigational drug can be found in the Investigator Brochure (IB). This information will be included in the patient informed consent and should be discussed with the patient during the study as needed. Any new information regarding the safety profile of the medicinal product that is identified between IB updates will be communicated as appropriate, for example, via an Investigator Notification or an Aggregate Safety Finding. New information might require an update to the informed consent and has then to be discussed with the patient.

The investigator must also instruct each patient to report any new adverse event (beyond the protocol observation period) that the patient, or the patient's personal physician, believes might reasonably be related to study treatment. This information must be recorded in the investigator's source documents; however, if the AE meets the criteria of an SAE, it must be reported to Novartis.

## 7.2 Serious adverse events

## 7.2.1 Definition of SAE

An SAE is defined as any adverse event [appearance of (or worsening of any pre-existing)] undesirable sign(s), symptom(s) or medical conditions(s)) which meets any one of the following criteria:

- is fatal or life-threatening
- results in persistent or significant disability/incapacity
- constitutes a congenital anomaly/birth defect
- requires inpatient hospitalization or prolongation of existing hospitalization, unless hospitalization is for:
  - routine treatment or monitoring of the studied indication, not associated with any deterioration in condition (specify what this includes)
  - elective or pre-planned treatment for a pre-existing condition that is unrelated to the indication under study and has not worsened since signing the informed consent
  - treatment on an emergency outpatient basis for an event not fulfilling any of the definitions of a SAE given above and not resulting in hospital admission
  - social reasons and respite care in the absence of any deterioration in the patient's general condition
- is medically significant, e.g. defined as an event that jeopardizes the patient or may require medical or surgical intervention.

All malignant neoplasms will be assessed as serious under "medically significant" if other seriousness criteria are not met.

Life-threatening in the context of a SAE refers to a reaction in which the patient was at risk of death at the time of the reaction; it does not refer to a reaction that hypothetically might have caused death if it were more severe (please refer to Annex IV, ICH-E2D Guideline).

Medical and scientific judgment should be exercised in deciding whether other situations should be considered serious reactions, such as important medical events that might not be immediately life threatening or result in death or hospitalization but might jeopardize the patient or might require intervention to prevent one of the other outcomes listed above. Examples of such events are intensive treatment in an emergency room or at home for allergic bronchospasm, blood dyscrasias or convulsions that do not result in hospitalization or development of dependency or abuse (please refer to Annex IV, ICH-E2D Guideline).

Any suspected transmission via a medicinal product of an infectious agent is also considered a serious adverse reaction.

## 7.2.2 SAE reporting

To ensure patient safety, every SAE, regardless of causality, occurring after the patient has provided informed consent and until 30 days after the last study visit must be reported to Novartis safety within 24 hours of learning of its occurrence. Any SAEs experienced after the 30 day period after the last study visit should only be reported to Novartis safety if the investigator suspects a causal relationship to study treatment.

All follow-up information for the SAE including information on complications, progression of the initial SAE, and recurrent episodes must be reported as follow-up to the original episode within 24 hours of the investigator receiving the follow-up information. An SAE occurring at a different time interval or otherwise considered completely unrelated to a previously reported one must be reported separately as a new event.

Information about all SAEs is collected and recorded on the Serious Adverse Event Report Form; all applicable sections of the form must be completed in order to provide a clinically thorough report. The investigator must assess the relationship of each SAE to study treatment, complete the SAE Report Form in English, and submit the completed form within 24 hours to Novartis. Detailed instructions regarding the submission process and requirements for signature are to be found in the investigator folder provided to each site.

Follow-up information is submitted as instructed in the investigator folder. Each reoccurrence, complication, or progression of the original event must be reported as a follow-up to that event regardless of when it occurs. The follow-up information should describe whether the event has resolved or continues, if and how it was treated, whether the blind was broken or not, and whether the patient continued or withdrew from study participation.

If the SAE is not previously documented in the Investigator's Brochure or Package Insert (new occurrence) and is thought to be related to the study treatment, a Drug Safety and Epidemiology Department associate may urgently require further information from the investigator for health authority reporting. Novartis may need to issue an Investigator Notification (IN) to inform all investigators involved in any study with the same study treatment that this SAE has been reported. Suspected Unexpected Serious Adverse Reactions (SUSARs) will be collected and reported to the competent authorities and relevant ethics committees in accordance with EU Guidance 2011/C 172/01 or as per national regulatory requirements in participating countries.

# 7.3 Reporting of study treatment errors including misuse/abuse

Medication errors are unintentional errors in the prescribing, dispensing, administration or monitoring of a medicine while under the control of a healthcare professional, patient or consumer (EMA definition).

Misuse refers to situations where the medicinal product is intentionally and inappropriately used not in accordance with the protocol.

Confidential

Abuse corresponds to the persistent or sporadic, intentional excessive use of a medicinal product, which is accompanied by harmful physical or psychological effects.

Study treatment errors and uses outside of what is foreseen in the protocol will be collected in the Dose Administration Record eCRF irrespective of whether or not associated with an AE/SAE, and reported to Safety only if associated with an SAE. Misuse or abuse will be collected and reported in the safety database irrespective of it being associated with an AE/SAE.

Table 7-1Guidance for capturing the study treatment errors including
misuse/abuse

Treatment error type	Document in Dose Administration (DAR) eCRF (Yes/No)	Document in AE eCRF	Complete SAE form
Unintentional study treatment error	Yes	Only if associated with an AE	Only if associated with an SAE
Misuse/Abuse	Yes	Yes,	Yes, even if not associated with a SAE

## 7.4 Pregnancy reporting

To ensure patient safety, each pregnancy occurring after signing the informed consent must be reported to Novartis within 24 hours of learning of its occurrence. The pregnancy should be followed up to determine outcome, including spontaneous or voluntary termination, details of the birth, and the presence or absence of any birth defects, congenital abnormalities, or maternal and/or newborn complications.

Pregnancy must be recorded on the Pharmacovigilance Pregnancy Form and reported by the investigator to the local Novartis Drug Safety and Epidemiology Department. Pregnancy follow-up should be recorded on the same form and should include an assessment of the possible relationship to the study treatment.

Any SAE experienced during the pregnancy and unrelated to the pregnancy must be reported on an SAE form.

## 8 Data review and database management

### 8.1 Site monitoring

Before study initiation, at a site initiation visit or at an investigator's meeting, a Novartis representative will review the protocol and data capture requirements with the investigators and their staff. During the study, Novartis employs several methods of ensuring protocol and GCP compliance and the quality/integrity of the sites' data. The field monitor will visit the site to check the completeness of patient records, the accuracy of data capture / data entry, the adherence to the protocol and to Good Clinical Practice, the progress of enrollment, and to ensure that study treatment is being stored, dispensed, and accounted for according to

specifications. Key study personnel must be available to assist the field monitor during these visits. Continuous remote monitoring of each site's data may be performed by a centralized Novartis CRA organization. Additionally, a central analytics organization may analyze data and identify risks and trends for site operational parameters, and provide reports to Novartis Clinical Teams to assist with trial oversight.

Confidential

The investigator must maintain source documents for each patient in the study, consisting of case and visit notes (hospital or clinic medical records) containing demographic and medical information, laboratory data, electrocardiograms, and the results of any other tests or assessments. All information on eCRFs must be traceable to these source documents in the patient's file. The investigator must also keep the original informed consent form signed by the patient (a signed copy is given to the patient).

The investigator must give the monitor access to all relevant source documents to confirm their consistency with the data capture and/or data entry. Novartis monitoring standards require full verification for the presence of informed consent, adherence to the inclusion/exclusion criteria, documentation of SAEs, and of data that will be used for all primary variables. Additional checks of the consistency of the source data with the eCRFs are performed according to the study-specific monitoring plan. No information in source documents about the identity of the patients will be disclosed.

# 8.2 Data collection

The trial (including the control cohort of healthy volunteers) will be conducted in a fully validated Data Capture system which conforms to US CRF 21 Part 11 requirements. Investigator site staff will not be given access to the system until they have been trained. Designated investigator staff will enter the data required by the protocol into the Data Capture system. Automatic validation programs within the system check for data discrepancies in the CRFs and by generating appropriate error messages, allow the data to be confirmed or corrected by the investigator staff. The investigator staff must certify that the data entered are complete and accurate. After database lock, the investigator will receive copies of the patient data for archiving at the investigational site.

Designated investigator staff will enter the data required by the protocol into the OC/RDC system. Designated investigator site staff will not be given access to the system until they have been trained.

Automatic validation procedures within the system check for data discrepancies during and after data entry and, by generating appropriate error messages, allow the data to be confirmed or corrected online by the designated investigator site staff. The Investigator must certify that the data entered into the electronic Case Report Forms are complete and accurate. After database lock, the investigator will receive copies of the patient data for archiving at the investigational site.

# 8.3 Database management and quality control

Novartis staff [or CRO working on behalf of Novartis] review the data entered into the CRFs by investigational staff for completeness and accuracy and instruct the site personnel to make any required corrections or additions. Queries are sent to the investigational site using an

electronic data query. Designated investigator site staff is required to respond to the query and confirm or correct the data. If the electronic query system is not used, a paper Data Query Form will be faxed to the site. Site personnel will complete and sign the faxed copy and fax it back to Novartis staff that will make the correction to the database. The signed copy of the Data Query Form is kept at the investigator site.

Concomitant medications entered into the database will be coded using the WHO Drug Reference List, which employs the Anatomical Therapeutic Chemical classification system. Concomitant procedures, non-drug therapies and adverse events will be coded using the Medical dictionary for regulatory activities (MedDRA) terminology.

Laboratory samples will be processed centrally and the results will be sent electronically to Novartis (or a designated CRO).

Randomization codes and data about all study drug(s) dispensed to the patient and all dosage changes will be tracked using an Interactive Response Technology (IRT). The system will be supplied by a vendor, who will also manage the IRT database. The database will be sent electronically to Novartis (or a designated CRO).

Each occurrence of a code break via IRT will be reported to the clinical team and monitor. The code break functionality will remain available until study shut down or upon request of Novartis.

The occurrence of relevant protocol deviations will be determined. After these actions have been completed and the database has been declared to be complete and accurate, it will be locked and the treatment codes will be unblinded and made available for data analysis. Any changes to the database after that time can only be made after written agreement by Novartis Development management.

## 8.4 Data Monitoring Committee

Not required.

# 8.5 Adjudication Committee

Not required.

# 9 Data analysis

A designated Contract Research Organization will perform the statistical analysis.

It is planned that the data from all centers that participate in this protocol will be combined, so that an adequate number of patients will be available for analysis.

The analysis will be conducted on all patient data at the end of Week 12 and at the time the trial ends at Week 53. Any data analysis carried out independently by the investigator should be submitted to Novartis before publication or presentation.

Efficacy, safety, and other data will be summarized for all weeks up to Week 53. For continuous variables, summary statistics (mean, standard deviation, median, 25th and 75th percentiles, interquartile range, minimum, and maximum) at each time point and for change

from baseline to each time point will be reported by treatment group. For discrete variables, frequency counts and percentages at each time point will be reported by treatment group.

Confidential

Primary efficacy variables will be summarized for lesional samples.

## 9.1 Analysis sets

The following analysis sets will be used for the statistical reporting and analyses:

Randomized Set: The Randomized Set includes all randomized patients.

Safety Set: The Safety Set includes all patients who received at least one dose of study medication. Patients will be included in the analysis according to treatment received.

Full Analysis Set: The Full Analysis Set comprises all patients to whom study medication has been assigned. Patients inappropriately randomized (e.g., IRT was called in error for randomization of a screen failed patient) will be excluded from this analysis set. Following the intent-to-treat principle, patients will be analyzed according to the treatment they were assigned to at randomization.

# 9.2 Patient demographics and other baseline characteristics

Data will be summarized by stratum with respect to demographic and baseline characteristics of all patients for the Randomized Set and the Full Analysis Set.

## 9.3 Treatments

The number of patients and the length of time (in days) exposed to each treatment will be summarized for the Safety Set.

Concomitant medications will be summarized by treatment using frequency counts and percentages for the Safety Set.

Any condition entered as medical history or current medical condition at baseline will be coded using the MedDRA dictionary for the Safety Set. They will be summarized by system organ class and preferred term of the MedDRA dictionary.

## 9.4 Analysis of the primary variable(s)

## 9.4.1 Variable(s)

Response of psoriasis skin lesions to treatment as measured by:

- a. Response in skin histology/K16 expression to treatment (yes, no)
- b. PASI 90 (yes, no)

The primary analysis time point will be at Week 12.

### 9.4.2 Statistical model, hypothesis, and method of analysis

For the two primary efficacy variables at each time point (response in skin histology/K16 expression to treatment at Week 12, PASI 90 at Weeks 4, 8, and 12), 95% confidence interval

for the difference between the two treatment groups with respect to the percentage of patients who have the "event" will be calculated using the normal approximation to the binomial distribution.

The primary analysis of the primary efficacy variables will be based on the Full Analysis Set.

## 9.4.3 Handling of missing values/censoring/discontinuations

For the two primary efficacy variables at Week 12 (and other time points), a patient with a missing assessment will be considered as a non-responder.

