### 9.4.4 Sensitivity analyses

The two primary efficacy variables will be analyzed at each time point for the Full Analysis Set using a logistic regression model with treatment and body weight (<90 kg,  $\geq$ 90 kg) as explanatory variables (Stokes, Davis, and Koch, 2012). The odds ratios and 95% confidence intervals for the odds ratios based on the fitted model will be reported.

Estimates of differences between the two proportions within each stratum will be calculated and examined for meaningful treatment-by-stratum interaction.

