2.5 Analysis of the primary objective

2.5.1 Primary endpoint

The primary efficacy variables are the response of psoriasis skin lesions to treatment as measured by:

- a) Response in skin histology/K16 expression to treatment (yes, no) (at Week 12)
- b) PASI 90 (yes, no) (at Weeks 4, 8, and 12)

The primary analysis time point will be at Week 12.

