2.5.2 Statistical method of analysis

• Response of skin histology/K16 expression to treatment (yes, no) (at Week 12)

Difference between the two treatment groups –(secukinumab 300 mg versus placebo) with respect to percentage of patients who have a negative ("no") response to skin histology/keratin 16 to treatment at Week 12, will be presented along with 95% confidence interval. Confidence interval will be calculated using normal approximation to the binomial distribution.

• PASI 90 (yes, no) (at Weeks 4, 8, and 12)

Same method of analysis as described above will be used for PASI 90 response (yes, no) at Weeks 4, 8, and 12.

The primary analysis of the primary efficacy variables will be based on the Full Analysis Set.

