2.5.3 Handling of missing values/censoring/discontinuations

For the primary efficacy variable K16 expression to the treatment at Week 12 (and other time points), a patient with a missing assessment will be considered as having a positive ("yes") response regardless of the reason for missing data (e.g., premature study discontinuation, missed visit, administrative issues). Patients who discontinue the trial for any reason will be considered as having a positive ("yes") response from the time they drop out through Week 52.

For the primary efficacy variable PASI90 response at Week 12 (and other time points), a patient with a missing assessment will be considered as a non-responder regardless to the reason for missing data (e.g., premature study discontinuation, missed visit, administrative issues). Patients who discontinuethe trial for any reason will be considered non-responders from the time they drop out through Week 52.

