2.5.4 Supportive analyses

Sensitivity analyses will be performed as follows:

The two primary efficacy variables will be analyzed at each time point (as describe in section 2.5.1) with non-responder imputation using a logistic regression model with treatment and body weight (< 90 kg, ≥90kg) as explanatory variables (Stokes, Davis, and Koch, 2012). The odds ratio and 95% confidence intervals for odds ratios (secukinumab 300 mg versus placebo) based on the fitted model will be reported.

In addition, estimates of differences between the two proportions within each stratum will be calculated using treatment-by-stratum interaction in the above model, separately. The odds ratio and 95% confidence intervals for odds ratios will be reported to examine meaningful treatment difference by strata.

This logistic regression analysis will not be performed if the data is sparse (quasi-separated or completely separated).

The sensitivity analysis will be done based on the Full Analysis Set.

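### No listed sensitivity analysis varies the missing-biopsy rule, so the visible plan cannot show how far technical sample loss moves the Week 12 K16/histology difference

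*Protocol*

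**What the plan says.** **Primary rule.** Protocol 9.4.3 covers both primary variables at Week 12 and other time points: "a patient with a missing assessment will be considered as a non-responder".

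**K16/histology in the SAP.** SAP 2.5.1 names the variable "Response in skin histology/K16 expression to treatment (yes, no) (at Week 12"). SAP 2.5.2 compares the arms on the "percentage of patients who have a negative ('no') response to skin histology/keratin 16 to treatment at Week 12". SAP 2.5.3 then says "a patient with a missing assessment will be considered as having a positive ('yes') response regardless of the reason for missing data", and its examples of reasons include missed visits and administrative issues. Patients who leave the trial take the same value through Week 52. For PASI 90, the same section makes a missing result a non-response.

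**Sensitivity analyses.** Protocol 9.4.4: "The two primary efficacy variables will be analyzed at each time point for the Full Analysis Set using a logistic regression model", with treatment and weight category as terms. SAP 2.5.4 runs that model "with non-responder imputation using a logistic regression model", adds a treatment-by-stratum version, keeps the Full Analysis Set, and drops the logistic analysis if the data are sparse or separated.

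**A conflicting line.** SAP 5.1.4 gives PASI-based responses multiple imputation or non-response, and gives other response variables LOCF.

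**Purpose.** SAP 5.4.1 plans no hypothesis test. Protocol 9.8 sizes the trial (50 and 25 patients) to estimate the difference in response rates.

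**The concern.** K16/histology depends on a punch biopsy (Protocol summary: Baseline, Week 12 and Week 52) that must be taken, shipped and read. When a patient leaves the trial, counting failure is defensible. When a sample is lost or unusable in a patient who is still in the trial, the gap says little about response, yet the rule treats both cases alike. The SAP itself expects omitted procedures in patients who stay in the analysis sets: deviation OTH04 in SAP Table 5-1 excludes a patient from nothing.

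The rule costs the placebo arm little, because few responses are expected there. In the secukinumab arm it removes responders in proportion to the loss. Since the estimate and its interval are the trial's product, a reader needs to see how much of the result depends on this rule. A weight-adjusted odds ratio computed on the same imputed data cannot show that.

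**Working it through.** **1. The plan's own precision figures.** Inputs are the arm sizes and percentages in Protocol 9.8, Table 9-1. The half-width is 1.96·√[p(1−p)(1/n₁+1/n₂)] + 0.5(1/n₁+1/n₂).

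- 50/25, p = 50%: 24.0 + 3.0 = 27.0 points. The column is 25.0/26.5/27.0/26.5/25.0, as stated.
- 66/33: 21.4/22.7/23.2/22.7/21.4, as stated.

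All ten entries match, but only with the continuity correction. The analysis text mentions no correction, so none is used below. With one, each interval would be 3.0 points wider on each side and coverage would be higher.

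**2. Which way the K16 rule points.** Read together, SAP 2.5.2 (arms compared on *no*), SAP 2.5.3 (missing = *yes*), SAP 2.5.4 (non-responder imputation) and Protocol 9.4.3 (missing = non-responder) fit if *no* is favourable. SAP 2.5.1 labels the variable as response to treatment, which suggests the reverse. The failure reading is therefore an inference.

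**3. Effect on the difference.** Let p_T and p_C be the response rates, and m_T and m_C the fractions lost independently of response.

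- Missing = failure: p_T(1−m_T) − p_C(1−m_C). With equal loss m this is (1−m)(p_T−p_C).
- Missing = success (the other label): [p_T(1−m)+m] − [p_C(1−m)+m], which is the same (1−m)(p_T−p_C) under equal loss. With unequal loss the label matters: at 80% vs 5% with 10% vs 20% lost, the result is 68.0 points under failure and 58.0 under success.

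**4. Size.** K16 and loss rates are assumptions. The only response rates in the documents are for PASI 90 (Protocol Table 3-1: 54–60% on secukinumab 300 mg, 0–2% on placebo). Coverage is the probability that the uncorrected normal-approximation 95% interval contains p_T−p_C, by exact binomial enumeration with 50 and 25 patients and equal loss.

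| True rates | Full-data difference | Expected difference at 5/10/15% loss | Coverage at 0/5/10/15% loss |
|---|---|---|---|
| 55% vs 2% | 53 | 50.4 / 47.7 / 45.1 | 95.2 / 94.3 / 90.4 / 83.0% |
| 70% vs 5% | 65 | 61.8 / 58.5 / 55.3 | 94.0 / 94.2 / 89.7 / 80.0% |
| 85% vs 5% | 80 | 76 / 72 / 68 | 92.5 / 93.8 / 85.5 / 67.6% |

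In simulations of the same settings with loss, the observed-case difference is unbiased and its interval covers 91–94%. At a 70% response rate, each lost secukinumab biopsy costs 70/50 = 1.4 points on average.

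**5. When shrinkage fails.** The difference grows if p_C·m_C > p_T·m_T. Placebo loss must then exceed secukinumab loss by the factor p_T/p_C: 16 at 80% vs 5%, 4 at 80% vs 20%. Example: 80% vs 20% with 5% vs 25% lost gives 76 − 15 = 61 points instead of 60.

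**6. What a sensitivity row would show.** Suppose 5 of 50 and 3 of 25 biopsies are lost, with 36/45 and 1/22 responding.

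- Observed cases: 80.0 − 4.5 = 75.5 points.
- Missing = failure: 36/50 − 1/25 = 68.0.
- Best case: 41/50 − 1/25 = 78.0.
- Worst case: 36/50 − 4/25 = 56.0.

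The listed analyses would report only the missing = failure data, on either scale.

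**7. LOCF.** No biopsy is scheduled between Baseline and Week 12, so LOCF has no post-baseline result to carry to Week 12. At Week 52 it could carry a Week 12 result, which contradicts SAP 2.5.3.

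**The case against.** The rule is prespecified, usual in this field and generally conservative for a claim of benefit. The study is exploratory and tests nothing. If the target is response with a result in hand, the interval estimates what was specified, and calling it biased presumes that technical loss ought to be missing at random. At 5% loss the shift is about 2.7 to 4.0 points against half-widths of about 13 to 15, and coverage is no worse than for observed cases (94.2/93.8/94.3% against 93.1/91.0/94.2% for 70% vs 5%, 85% vs 5% and 55% vs 2%). No passage supports 10–15% technical loss. This stands, and it is why the primary rule should stay. It does not supply a check on that rule.

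A reader might infer more than the documents support:

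- *Every planned analysis scores a lost biopsy as failure.* SAP 5.1.4 on its face assigns LOCF to K16. The Protocol summary mentions cross-classification tables and a logistic model using K16 in partly cut text, and some exploratory sections are not visible.
- *The SAP says failure for K16.* It says *yes*, with the polarity undefined.
- *The effect must shrink.* That needs broadly similar loss in the two arms.
- *Nothing would reveal the loss.* SAP 2.3.1 tabulates discontinuations and deviations by arm, and OTH04 would capture some procedures not done. That is partial visibility, and it would not clearly include samples lost in shipping or reading.

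**Conclusion.** The point holds for the visible Week 12 analyses of the treatment difference. A missing K16 result counts as non-response whatever the reason, taking *no* as favourable, and neither listed sensitivity analysis changes that. With response-unrelated loss of similar size m in both arms, the difference is multiplied by about (1 − m). This is minor at 5% loss and material at 10–15%: coverage is about 86–90% and 68–83% under the assumed response rates. The actual loss rate is unknown, so this is a case for showing the dependence. It is not evidence that the result will be wrong. The multiple imputation that SAP 5.1.4 mentions for PASI is not used in any visible analysis, so PASI 90 has the same gap. The change is worth making, and the primary rule need not be replaced.

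**What to change.** 1. Keep missing = failure as the primary rule.
2. In SAP 2.5.1 to 2.5.3, state which K16 label is favourable. Reconcile SAP 2.5.3, 2.5.4 and 5.1.4 with each other and with Protocol 9.4.3.
3. In Protocol 9.4.4 and SAP 2.5.4, add one supportive Week 12 analysis for K16/histology, and the same for PASI 90. Patients who left the trial remain failures. Results missing for technical or administrative reasons in patients still in the trial (not taken, lost, unreadable, missed visit) are treated as missing at random, by either the observed-case risk difference with 95% CI or multiple imputation by arm and weight stratum.
4. Report the number missing by arm and reason beside both estimates.

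The cost is SAP wording, a reason flag for missing biopsies and one more table row, with no change to sample size. The downside is that the added estimate assumes technical loss is unrelated to response, so it should stay supportive.
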